**North Carolina Prostate Cancer Comparative Effectiveness &
Survivorship Study (NC ProCESS)**

National Clinical Trial (NCT) Identification Number: NCT02564120

Principal Investigator: [name]

1 Jan 2019

Study Protocol

Brief Summary:

NC ProCESS is a cohort of patients from diverse backgrounds diagnosed with early prostate cancer, who were enrolled from January 2011-June 2013. These patients were recruited throughout North Carolina, and also in partnership with institutions across the country. Patients enrolled before they start treatment, and are then followed prospectively through treatment and then afterwards. This observational study collects information on quality of life, cancer control, and health care received inclusive of treatment and management of subsequent effects including complications and recurrence. The objective of this study is to examine comparative outcomes among different modern prostate cancer treatment options in this cohort of patients.

Detailed Description:

Localized prostate cancer treatment options is consistently a "highest priority" comparative effectiveness research (CER) topic according to the Institute of Medicine, Agency for Healthcare Research and Quality (AHRQ), and other summary reports. Patients urgently need information on the comparative outcomes of modern treatment options to guide decision-making for this disease that causes significant burden based on its high prevalence, mortality and treatment effects on quality of life. The status quo as it pertains to prostate cancer is significant overtreatment causing potential patient harm, rapid diffusion of new/expensive technologies without proven benefit and patients lacking high quality research evidence to balance direct-to-consumer advertising and guide individualized decision-making.

NC ProCESS is a population-based cohort designed specifically to address well-described knowledge gaps. It was designed in close collaboration with the unique AHRQ consortium stakeholder group, which included representatives from patients, clinicians and policymakers. Stakeholders helped define study design to emphasize "real-world" patients and select patient-centered and relevant outcomes, and have been involved throughout assembly of this patient cohort. The diverse cohort is well-represented by "hard to reach" patients; enrollment before treatment avoids biases with participation and recall. As clinical trials are not feasible to address the central questions in prostate cancer CER, this prospective study will yield the

highest level of evidence to inform patients and other stakeholders. With an assembled cohort, this study is necessary to examine comparative outcomes.

Study Design:

Study Type:	Observational
Actual Enrollment:	1656 participants
Observational Model:	Cohort
Time Perspective:	Prospective
Study Start Date:	January 2011
Estimated Primary Completion Date:	December 2018
Estimated Study Completion Date:	December 2018

Outcome Measures:

Primary Outcome Measure:

1. Patient Reported Outcomes [Time Frame: 4 years]
Directly compare patient-reported prostate-cancer specific and global quality of life (QOL), anxiety regarding prostate cancer and decisional regret in a cohort of men with localized prostate cancer managed by active surveillance, radical prostatectomy, radiation therapy, and brachytherapy.
2. Disease-Free Survival [Time Frame: 5 years]
Directly compare the disease-free survival among different treatment options for prostate cancer.
3. Directly compare health care utilization among different treatment options for prostate cancer from review of medical records [Time Frame: 4 years]
For each treatment group (radiation therapy, prostatectomy, active surveillance), we will describe the cumulative utilization for each category of health care. These categories are physician/specialty visits, hospitalizations, diagnostic tests/procedures, medications, and prostate cancer treatments (for the initial cancer and for recurrence).
Measurements will be attained by review of medical records.

Eligibility Criteria:

Ages Eligible for Study:	35 Years to 80 Years
Sexes Eligible for Study:	Male

Accepts Healthy Volunteers: No
Sampling Method: Non-Probability Sample

Study Population

Newly-diagnosed, early stage (localized, non-metastatic) prostate cancer patients

Inclusion Criteria:

- Newly-diagnosed, histologically-proven, localized prostate adenocarcinoma.
- Completion of baseline interview prior to initiating therapy.
- Patient ability to complete study interview: no cognitive impairment, language or hearing problems.
- Not diagnosed with prostate cancer through transurethral resection of the prostate (TURP).
- Age 35-80.
- English speaking.
- Has telephone.

Exclusion Criteria:

- Initiation of treatment for prostate cancer prior to completion of baseline interview.
- Cognitive impairment.
- Hearing problems.
- Inability to speak or understand English.

Analytical and Statistical Approaches

Aim 1: Consistent with the prostate cancer QOL literature, we treated each patient-reported outcome measure as a continuous variable. We described the mean, standard deviation, and range of each measure at each time point, as well as the change from each time point compared to the baseline measure. Differences among treatment groups were compared using t-tests. A unique aspect of the PCSI instrument is that scores in each domain (Urinary Incontinence, Urinary Obstruction/Irritation, Bowel Problems, Sexual Dysfunction) are translatable into functional categories: normal, intermediate, and poor.^{2,37} Thus, we explored QOL measures using functional categories to facilitate creation of patient-friendly dissemination materials that summarize study findings. Further, to examine differences in outcomes across treatments, we conducted linear regression models applying propensity scores; a separate model was constructed for each outcome measure. We used generalized estimating equations (GEE) to account for correlation of the outcome measured repeatedly over time. In addition, we included time as a categorical variable and added a time*treatment interaction in the models to account for a non-linear change in outcome over time.

Aim 2: We estimated DFS at 5 years among different treatment groups, using the Kaplan-Meier product-limit estimate of the survival curve. We also used the logrank statistic to assess for differences in DFS among the different treatment groups. Cox proportional hazards models were performed with the application of propensity scores. These Cox models estimated the hazard rate for each treatment type and evaluated differences in rates (rate ratios) between treatments, adjusting for confounding using propensity scores. We examined the proportional hazard assumption in each model and included time-varying covariates or incorporated a time*treatment interaction into the model when this assumption was not met.

Aim 3: We described the cumulative utilization for each category of health care (physician/specialty visits, hospitalizations, diagnostic tests/procedures, medications, prostate cancer treatment) within 4 years by treatment group. Specifically, we examined the proportion of patients in each treatment group who received each category of care (we created a

dichotomous variable indicating whether the patient received the care), and the count of services in each care category. We tested the differences in proportions between treatment groups using chi-square tests and differences in counts between treatment groups using t-tests. In multivariable analyses, we used logistic regression models and propensity score methods to estimate differences among groups in the proportions of patients receiving each category of care. Linear regression models incorporating propensity score methods were used to test differences among groups in the number of services received in each category. When counts of health care utilization were small (e.g., hospitalization) Poisson regression models were used.

Bias and Confounding: The use of the NCCCR RCA enabled all study participants to enroll prior to the initiation of treatment, thereby avoiding potential biases related to participation based on post-treatment outcomes. Furthermore, all baseline QOL data were collected before treatment, avoiding biases inherent to the recall of baseline information due to patient experiences during and after treatment. The following analytical methods were also employed to minimize and account for potential bias and confounding.

1. **Propensity score methods:** We conducted propensity score analysis to assess for potential bias from measured confounders between treatment groups. Specifically, we used logistic regression to estimate the probability of receiving each treatment based on baseline characteristics and compute the propensity score from the model predicted probability of treatment for each participant. We examined the distribution of propensity scores across treatment groups and trimmed observations from the non-overlapping ends of the distribution as appropriate.⁵⁷ We then created inverse probability of treatment weights (IPTW) and stabilized these weights to reflect the sample size of each treatment group. IPTW was used in multivariable analyses to maximize the balance of confounding variables between the treatment groups. Propensity score matching using a “greedy algorithm”⁵⁸ and an alternative “optimal match”⁵⁹ algorithm was also considered as an approach to balance covariates across treatment groups.

2. **Assessment of sample balance:** To ensure balance of sample characteristics, we compared differences between treatment groups in the mean (for continuous variables) or distribution (for categorical variables) of each covariate by applying the generated propensity score weights. In addition, for propensity score-matched samples, we assessed the balance of study covariates using standardized differences across treatment groups. We added interaction terms to the propensity score model for the sample characteristics and risk factors that remained unbalanced after applying initial propensity score methods. When imbalances remained, we included the unbalanced variables in the multivariable outcome model(s) to ensure proper control of these confounding factors.
3. **Instrumental variables (IV):** We explored instrumental variable approaches to estimating the relationship between treatment and outcome while addressing potential unmeasured confounders. This method requires finding an appropriate “instrument” that is related to the exposure (treatment) but not directly related to the outcome, and meets all underlying IV assumptions.⁶⁰
4. **Handling of missing data:** We followed the PCORI standards for handling and minimizing the impact of missing data. First, we carefully examined the pattern of missing data by individual items. We determined whether the missing data is informative, missing not at random (MNAR), missing completely at random (MCAR), or missing at random (MAR) by evaluating patient characteristics (e.g., age, race and ethnicity, treatment). We also compared those patients with missing data to patients with complete data. We then imputed missing data using a widely-employed multiple imputation approach.⁶¹ This method replaces the missing data with a set of m possible values by creating m imputed datasets through Monte Carlo technique. Each imputed dataset was analyzed using the same methods that are used for complete datasets. Results were pooled together to provide valid statistical inferences.⁶¹ These methods enabled us to use data from the entire study sample, including patients with differential follow-up, maximizing the study’s statistical power to detect differences among

treatment groups. Lastly, we conducted sensitivity analyses to examine the impact of the missing data on study results.^{62–65}

5. **Cluster analysis:** We examined for possible clustering within our study sample as data may have been clustered at several levels. For example, patients treated by the same physicians or facilities may have correlated outcomes, and patients living in the same area may share characteristics related to treatment outcomes. To account for clustering in our analysis of DFS (Aim 2), we conducted proportional hazard model using a robust sandwich estimate⁶⁶ and likelihood-based random effect (frailty) model.⁶⁷ For outcomes analyzed by linear and logistic regression models, we used GEE modeling approaches to obtain appropriate standard errors, and/or applied multilevel modeling to explicitly model the clustered data structures and allow for random intercepts of the higher level data structure.

Evaluation of Treatment Outcome Heterogeneity: Our rich cohort comprised a sizable proportion of understudied populations, including patients of racial/ethnic minorities, lower socioeconomics, and rural/underserved areas. Therefore, we sought to assess heterogeneity of treatment effect (HTE) following PCORI guidelines. We performed descriptive HTE analysis to produce effect estimates and standard errors for key confounders (e.g., race and ethnicity, age, disease severity). We also explored subgroup analyses when sample size permitted enough power to detect meaningful differences.

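### Do the differing treatment-group lists and the undefined disease-free survival endpoint call for a change to the plan?

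*Combined protocol and SAP*

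**What the plan says.** The group lists are in Outcome Measures. Outcome 1 (patient-reported outcomes) concerns men with "localized prostate cancer managed by active surveillance, radical prostatectomy, radiation therapy, and brachytherapy", which is four groups. Outcome 3 (utilization) reads "For each treatment group (radiation therapy, prostatectomy, active surveillance), we will describe the cumulative utilization for each category of health care", which is three, with brachytherapy not mentioned. Outcome 2 says only "Directly compare the disease-free survival among different treatment options for prostate cancer".

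Aim 2 of the Analytical and Statistical Approaches is no more specific: "We estimated DFS at 5 years among different treatment groups, using the Kaplan-Meier product-limit estimate of the survival curve". It adds logrank tests and propensity-adjusted Cox models. It does not say what counts as an event, when time starts or when a man is censored.

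Under Bias and Confounding, item 1 says "we used logistic regression to estimate the probability of receiving each treatment based on baseline characteristics" and that the analysts would "compute the propensity score from the model predicted probability of treatment for each participant". The weights are stabilised by group size, and "IPTW was used in multivariable analyses to maximize the balance of confounding variables between the treatment groups". The treatments are not listed there. Item 2 compares weighted covariates between treatment groups, adds interactions to the propensity model where balance is poor, and puts any covariate still unbalanced into the outcome model.

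**The concern.** Two gaps seem to combine. First, if brachytherapy is pooled in Outcome 3, the term radiation therapy has two meanings within one list of primary outcomes. If it is not pooled, brachytherapy patients have no group in Outcome 3. The propensity section does not settle which list it follows. Had the score been fitted on three groups, the quality-of-life comparison of radiation with brachytherapy would not be adjusted by the weights. The plan's own balance check, run on the same three groups, would look satisfactory.

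Second, DFS is a primary outcome, and a 5-year estimate depends on the event definition. This matters most for active surveillance, where a later move to treatment might or might not count as an event. A reader with only this document could not reproduce the Kaplan-Meier estimates or the Cox rate ratios.

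**Working it through.** The plan has no sample-size or power figure on this point to reproduce. The check has three parts.

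**1. What three-group and four-group weights do.** Inputs from the documents: four groups in Outcome 1, hence C(4,2) = 6 pairwise contrasts; three in Outcome 3, hence C(3,2) = 3. Let e_k(X) be the probability of group k given covariates X, p_k its marginal share, R radiation and B brachytherapy.

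- Three-group stabilised weight, the same for R and B: (p_R + p_B) / (e_R(X) + e_B(X)). The weighted odds of R against B at X are therefore e_R(X)/e_B(X), exactly the unweighted odds. Only prostatectomy versus surveillance, 1 of the 6 contrasts, is balanced by construction. The pooled R+B group is balanced too, so a three-group check passes if the propensity model is correct.
- Four-group stabilised weight: p_k / e_k(X). The covariate density in group k is f(X)·e_k(X)/p_k, and multiplying by the weight gives f(X), the cohort distribution. This holds for every group and for any pooled set of groups. One set of four-group weights therefore serves all 6 contrasts of Outcome 1 and all 3 of a pooled Outcome 3.

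A simulation on assumed inputs agrees. It used 200,000 men, one standardised confounder, and shares of about 0.29 surveillance, 0.37 prostatectomy, 0.25 radiation and 0.09 brachytherapy. The rows differ in how far brachytherapy's log-odds slope on the confounder was set below radiation's.

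| Slope difference | R–B difference, unweighted (SD) | Three-group weights | Four-group weights |
|---|---|---|---|
| 0.25 | 0.21 | 0.24 | 0.00 |
| 0.50 | 0.42 | 0.47 | 0.00 |
| 1.00 | 0.84 | 0.84 | 0.01 |

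The mechanism is real, and its size depends wholly on the assumed slopes.

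**2. Whether the plan puts the study in the harmful case.** Three things must all happen: four groups are compared, the weights are fitted on three, and balance is checked on three. No section says this. Item 1 models each treatment and aims at balance between the treatment groups. For Outcome 1 those groups are listed, and there are four. The three-group list belongs to the utilization outcome, where pooling brachytherapy with external radiation is the natural reading and a legitimate coarser grouping. That list also shortens radical prostatectomy to prostatectomy, so its labels are abbreviated in any case. By part 1, the two lists do not need two propensity models.

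**3. DFS.** Outcomes 2 and 3 use the same phrase for the options compared, and Outcome 3's list includes active surveillance, so surveillance appears to be in the DFS comparison as well. Brachytherapy's place there is not stated.

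The choice of event can matter. Assume 5-year progression q of 2% to 10%, conversion from surveillance to treatment c of 20% to 50%, and independence.

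- Conversion not an event: DFS is 1 − q, or 90% to 98%.
- Conversion an event: DFS is (1 − q)(1 − c), from 0.90 × 0.50 = 45% to 0.98 × 0.80 = 78%.

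The choice of origin matters less. With constant hazard, an assumed lag of 3 to 9 months and 5-year DFS of 80% to 90% from treatment, counting from diagnosis moves the estimate by about 0.5 points (0.900 to 0.905) to 2.7 points (0.800 to 0.827).

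Follow-up is not a constraint. June 2013 to December 2018 is 66 months, so 60 months from enrolment is covered for the last entrants with 66 − 60 = 6 months to spare, if follow-up ended at the estimated completion date. A shorter span counted from treatment start would ordinarily be censored, which Kaplan-Meier and Cox handle. The missing-data item examines missingness item by item and does not say that DFS times were imputed.

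**The case for a change.** The strongest case for a change is that DFS is a primary endpoint and its definition is simply absent. The illustration above moves 5-year surveillance DFS from 90–98% to 45–78% on that choice alone. The propensity section is also silent on its groups, so the safeguard in item 2 protects the radiation-versus-brachytherapy comparison only if it was run on four groups, and the text does not prove that it was. Stating these things would cost a few sentences.

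The factual part stands: the definitions and group lists are not in the document, and nothing marks them as redacted. What does not stand is the step from there to a faulty plan. The weighting harm requires a mismatch that the text does not describe and that a competent analyst would not ordinarily introduce. The DFS figures rest on assumed rates, and they show that the definition matters, not that a wrong one was used. Either grouping for utilization would be acceptable. The document is dated 1 January 2019 and describes its analyses in the past tense, so writing definitions into it now would record choices already made rather than alter any analysis. Those definitions belong with the reported results.

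**Conclusion.** No change to the plan follows. The four-versus-three difference is most likely a coarser label for utilization. The unlisted propensity groups and the undefined DFS event, origin and censoring are details that analysts fill sensibly, and no rule that the plan states is shown to produce a wrong answer.

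This rests on two readings: that the weights and the balance check for Outcome 1 used its four listed groups, and that DFS was defined on the same basis in every group. If the first proved false, 5 of the 6 Outcome 1 contrasts would not be balanced by construction, and radiation versus brachytherapy would be no better adjusted than without weights. The documents give 1656 participants with no split by treatment and no event rates, so no size can be put on that possibility. A reader of the results should look there for the DFS definition and the groups used before interpreting the 5-year estimates.

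### Aim 3's yes/no prostate cancer treatment variable includes the initial treatment: if groups are treatments received, radiation v prostatectomy cannot be tested and the test against surveillance is settled by the group label

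*Combined protocol and SAP*

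**What the plan says.** All references are to the combined protocol and SAP.

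- **Outcome Measures, primary outcome 3**, compares radiation therapy, prostatectomy and active surveillance over 4 years on five categories of care. The fifth is "prostate cancer treatments (for the initial cancer and for recurrence", so initial and later treatment form one category.
- **Brief Summary** places the initial treatment inside follow-up: "Patients enrolled before they start treatment, and are then followed prospectively through treatment and then afterwards". The inclusion criteria agree, since the baseline interview must precede therapy.
- **Analytical and Statistical Approaches, Aim 3**, lists prostate cancer treatment among the categories and gives each a "dichotomous variable indicating whether the patient received the care". On testing: "We tested the differences in proportions between treatment groups using chi-square tests and differences in counts between treatment groups using t-tests". On adjustment: "we used logistic regression models and propensity score methods to estimate differences among groups in the proportions of patients receiving each category of care". No category is exempted, and initial treatment is not taken out.
- **Bias and Confounding, item 1**, is the nearest thing to a grouping rule. The propensity model is used to "estimate the probability of receiving each treatment based on baseline characteristics". No section says how men are assigned to groups, or how surveillance men who are treated later are handled.

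**The concern.** For this category, the event that puts a man in a treated group is also the event that scores him yes on the outcome. The planned test then has nothing to estimate between the two treated groups, and against surveillance it mostly restates the group definition.

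What can differ between radiation and prostatectomy is treatment after the index course. Patients choosing between them would want to know it, and the combined yes/no variable hides it. There is also a reporting risk: a very small p-value against surveillance could be presented as a finding when the group label produced it.

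**Working it through.** The documents give no sample size, significance level, group sizes or utilization rates for Aim 3, so there is no stated figure to reproduce.

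**Inputs.** From the documents: 1656 enrolled and three groups in outcome 3. Assumed: equal groups, 1656/3 = 552; a 5% two-sided level; 20%, 30% or 40% of men initially on surveillance treated within 4 years (110, 166 or 221 of 552); all other rates below.

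**1. Groups are treatments received: radiation v prostatectomy.** The table is 552 yes, 0 no against 552 yes, 0 no. Each expected no count is 552 × 0/1104 = 0, so Pearson's chi-square divides by zero and is undefined. This holds at any group size. Propensity weighting does not help, because there is no man in the empty cells to weight.

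**2. Same grouping: test against surveillance.** With k untreated surveillance men and equal groups, the three-group chi-square (2 df) reduces to 2 × 1656 × k/(1656 − k).

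| Surveillance men treated | k | Chi-square | 100% minus surveillance share |
|---|---|---|---|
| 110 (19.9%) | 442 | 1206 | 80.1 points |
| 166 (30.1%) | 386 | 1007 | 69.9 points |
| 221 (40.0%) | 331 | 827 | 60.0 points |

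The critical value is 5.99. At k = 3 the statistic is 2 × 1656 × 3/1653 = 6.01 (p=0.0495); at k = 2 it is 2 × 1656 × 2/1654 = 4.00. The test therefore stops rejecting only when at least 550 of 552 surveillance men (99.6%) are treated. That boundary is rough, since expected no counts are about 1 per group. If surveillance means never treated in the window, the comparison is 0% v 100% by definition.

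**3. Logistic model.** For 552/552 v 166/552 the profile log-likelihood is −345.83, −337.59 and −337.54 at log odds ratios of 5, 10 and 20. It keeps rising, so no finite estimate exists. The difference in proportions is finite.

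**4. Groups follow initial choice.** Suppose 6 or 28 of 552 men who chose active treatment did not receive it. Their proportions are 546/552 = 98.9% or 524/552 = 94.9%. Against 30.1% in surveillance, the differences are 68.8 or 64.9 points. Radiation v prostatectomy can now be computed, but its yes/no result reflects whether men received what they chose.

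**5. What the variable hides.** Assume later treatment in 28/552 (5.1%) v 55/552 (10.0%). With the index course included, both groups show 100%. Without it:
- difference 27/552 = 4.9 points, 95% CI 1.8 to 8.0;
- odds ratio (55 × 524)/(28 × 497) = 2.07, 95% CI 1.29 to 3.32;
- chi-square 9.50, p=0.002.

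**6. Counts.** If each course is one service and each treated man has one index course, the totals are 552 + 28 = 580 and 552 + 55 = 607. Adding 1 to every man's count changes neither the difference in means nor its variance, so the t-test is the same with or without the index course (difference 0.049, t=3.09, p=0.002). The ratio of cumulative counts is 607/580 = 1.05; the ratio for later treatment alone is 55/28 = 1.96.

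**The case against.** The strongest reply is that the problem shows itself and is small. A 100% v 100% table yields no test and so no false conclusion, and any analyst would notice a log odds ratio that does not converge. The outcome is framed as description, the surveillance proportion is informative, and the count t-test can still find a difference between treated groups. Only one yes/no variable, in one of five categories of one of three primary outcomes, is affected. The 100% figure also depends on a grouping rule that the documents do not give.

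Much of this stands, and it limits the scope. It does not remove the defect: Aim 3 prescribes a test and a logistic model for every category, and for this one they are degenerate or nearly so under either grouping.

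A reader might infer more than the documents support in two places.

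- *That the count analysis also fails.* Aim 3 says "When counts of health care utilization were small (e.g., hospitalization) Poisson regression models were used", and a Poisson model with model-based standard errors would give p=0.43 for the counts in step 6. That requires courses as the counting unit, the small-count rule applying here, and model-based standard errors despite weighting. None of these is stated. The cluster section's "For outcomes analyzed by linear and logistic regression models, we used GEE modeling approaches to obtain appropriate standard errors" does not show that Poisson models went without such errors, and a robust standard error gives p=0.002. Nor is 1.05 biased: it is the correct ratio for cumulative use, simply not a description of later treatment.
- *That the other four categories share the fault.* Nothing in the documents shows this.

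**Conclusion.** The point holds for the yes/no variable of this one category and should be fixed. If groups are treatments received, the undefined radiation v prostatectomy test and the absence of a finite log odds ratio against surveillance (as long as some surveillance men are untreated) follow from the definitions and need no assumed rates. The chi-square values of 827 to 1206 rest on 552 per group and 20% to 40% of surveillance men treated. If groups follow initial choice, the fault weakens to a contrast with surveillance that mainly reflects adherence to that choice.

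It does not follow that Aim 3 has no usable result here. The share of surveillance men treated within 4 years is not fixed by the label when the group is defined by initial management, and it is useful as description. The count analysis may still detect a difference in later treatment.

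**What to change.** For this category:

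1. State how men are assigned to groups, and one time origin for the 4 years that is the same in every group.
2. Report initial treatment descriptively, without a test.
3. Test a yes/no variable, and a count, for prostate cancer treatment after the index course, among the actively treated groups only. Count planned combined treatment as part of the index course.
4. Report the proportion of surveillance men treated within 4 years with a confidence interval, as description; for example 166/552 = 30.1%, Wilson 95% CI 26.4% to 34.0%.

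**Cost.** This needs SAP wording, recoding and a rerun of one category. The plan is written in the past tense and dated after the estimated completion date, so the change may be a re-analysis and should be labelled as such. It requires that the record abstraction separates the index course from later treatment, which the documents do not confirm. There would be no p-value or odds ratio against surveillance for this category.

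The later-treatment test also has fewer events. Taking power as Φ(|p1 − p2|/√[(p1(1 − p1) + p2(1 − p2))/552] − 1.96), with an assumed 552 per group and no weighting, it is 71% for 10% v 15%, 59% for 15% v 20%, and above 99% for 10% v 20%.
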